2.3 Tertiary comparisons

The primary outcome will also be assessed in the following subgroups (at 2 years after transplantation and after a median follow-up of 5 years):

- Induction therapy allocation
- Men and women
- Age (<60, ≥60 years)
- Deceased brain death, deceased cardiac death and living donors
- Categories of HLA mismatch defined by NHSBT allocation categories: 1 (no mismatches); 2 (0 DR and 0 or 1 B mismatches); 3 (0 DR and 2B, or 1 DR and 0 or 1 B mismatches); 4 (1 DR and 2B, or 2 DR)
- Sensitization status (high versus normal determined by calculated reaction frequency)
- First and subsequent transplants
- Categories of baseline graft function (eGFR <40, ≥40 <60 and ≥60 mL/min)
- Categories of baseline proteinuria (urine protein:creatinine ratio <30, ≥30 <50, ≥50 mg/mmol)

Exploratory analyses will also be undertaken of reported serious adverse events, non-serious adverse reactions and laboratory results (with due allowance made in their interpretation for the retrospective and exploratory nature of such analyses).

3 Details of analyses

3.1 Methods of analysis

The fundamental assessments of efficacy and safety will involve comparisons among all randomized patients in their originally allocated treatment group (i.e. “intention to treat” analyses).^{1, 2} Analyses of categorical outcomes will be based on the first relevant unrefuted event of a particular type (i.e. either confirmed or not refuted during the adjudication process). All time-to-event analyses will be based on the first relevant event, and will use log-rank methods to calculate average event rate ratios (95% confidence intervals) and their associated 2-sided P-values.^{2, 4} Comparisons of continuous outcomes will adjust for the baseline value if available, otherwise two-sample t-tests will be used.

The primary comparison between treatment groups of mean follow-up eGFR at 2 years post-transplantation (ie, on average 18 months post maintenance randomisation) will use analysis of covariance (ANCOVA), adjusted for the baseline value.⁵ The baseline creatinine value used will be the latest value available prior to the maintenance randomisation (including a value from a sample

taken on the day of that randomisation). Any value within 6 months of the anniversary of the date of transplantation will be considered as that year's value. If multiple results are available within this window, the one closest to the anniversary date will be used.

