## **2.5 SAMPLE SIZE CALCULATIONS**

The 3C study sample size is determined by the maintenance therapy allocation. A meta-analysis of the effect of conversion to sirolimus-based maintenance therapy showed an improvement in eGFR of 6.4 mL/min (95% CI 1.9-11) in the group assigned to sirolimus (12). The trials included in this meta-analysis varied in duration, with most patients followed for one year. If these differences could be maintained, it would be reasonable to anticipate a 10 mL/min difference in GFR two years after conversion to sirolimus (i.e. median follow-up at least 2.5 years after transplantation). Adherence to sirolimus therapy is likely to be around 75% (i.e. approximately 25% of patients allocated sirolimus in randomised trials discontinue it (12)) and this must be taken into consideration.

800 patients would have excellent power (>90%) with  $\alpha = 0.05$  and good power (>80%) with  $\alpha = 0.01$  to detect such a difference when allowance is made for the likely proportion of patients who are ineligible for the second randomisation and adherence with sirolimus.

800 patients would also provide good power (90%) with  $\alpha = 0.05$  to detect a halving in the acute rejection rate at six months (from 15% to 7.5%), which is the primary comparison in the induction therapy comparison.

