#### 3.4.2 *Current medication and clinical measurements*

The patient's current medication will be recorded. Blood pressure will be recorded at all follow-up visits and weight recorded at 6 and 12 months..

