### 3.5 **SECOND RANDOMISATION (at ~6 months)**

The second randomisation (between sirolimus- and tacrolimus-based maintenance therapy) can occur from 5 to 7 months post-transplantation (ideally to coincide with 6 month follow-up visit). The following exclusion criteria will apply:

- proteinuria >800 mg/day (or protein:creatinine ratio >80 mg/mmol);
- biopsy-proven acute rejection (Banff score >1) in previous month.

(See section 3.5.1 for guidance on the management of patients who are not willing and eligible for second randomisation or whose local investigator does not consider it in their best interests.)

In order to minimise the impact of this exclusion criterion, investigators will be encouraged to monitor proteinuria and treat it appropriately (with ACE inhibitors and/or angiotensin receptor blockers) during the first six months post-transplant surgery.

The second randomisation will be stratified by induction therapy allocation and minimized by prognostically-relevant criteria including graft function, proteinuria and blood pressure.

Investigators should only randomise patients for whom they remain uncertain about the benefits of CNI-based or sirolimus-based maintenance treatment. Patients with reduced graft function (e.g. eGFR <40 mL/min/1.73m^2) will not be routinely excluded, but their events in this subgroup will be monitored closely by the independent Data Monitoring Committee.

Patients will be allocated to either remain on tacrolimus (all patients to have target trough level 5-7 ng/mL) or convert to sirolimus. The target trough level for sirolimus is 6-12 ng/mL for the first six months (patients who received basiliximab induction should be maintained at the upper end of this range) and thereafter 5-10 ng/mL.

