Campath, Calcineurin inhibitor reduction and Chronic allograft nephropathy

Data Analysis Plan for assessing clinical efficacy and safety of sirolimus-based maintenance treatment in the 3C Study

1 Background

This Data Analysis Plan describes the strategy, rationale and statistical methods that will guide assessment of the clinical efficacy and safety of sirolimus-based maintenance therapy in the 3C Study. A separate Data Analysis Plan will describe the assessment of Campath-based induction therapy. All analyses and reports will be prepared by the coordinating centre in the Clinical Trial Service Unit, University of Oxford.

The 3C Study is a randomized trial investigating two strategies to improve long-term outcomes in kidney transplantation. Firstly, it is comparing Campath (alemtuzumab) with basiliximab as the basis of induction therapy. Secondly, it is comparing an elective conversion to sirolimus-based maintenance therapy at around 6 months after transplantation compared to remaining on tacrolimus-based maintenance therapy. Follow-up visits are scheduled at 1, 3, 6, 9 and 12 months after transplantation and will then be followed by annual mailed questionnaires. In addition, all participants will be flagged with various NHS registries.

2 Comparisons of sirolimus-based versus tacrolimus-based maintenance therapy

All comparisons will involve comparing outcome during the defined analysis period among all those participants allocated at the maintenance randomization to receive sirolimus-based induction versus all those allocated to receive tacrolimus-based maintenance therapy (i.e. “intention-to-treat” analyses).^{1, 2} All analyses will be stratified by induction therapy arm.

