3.2 Missing data

It is likely that values of creatinine will be missing at random (as they will be collected via the UK Transplant Registry and it is very unlikely that their randomized allocation would affect whether a hospital provides data to the registry). Baseline characteristics of those participants with available and those participants with missing data will be compared to identify any characteristics associated with missingness. The amount of missing data at various timepoints after transplantation will be displayed graphically.

Missing eGFR values will be imputed using a multiple imputation model, using baseline covariates of:

- Age (calendar year)
- Sex
- Type of transplant (living donor, donor after brain death and donor after cardiac death)
- Donor age (calendar age)
- Proteinuria at baseline (in categories: ≤ 30 mg/mmol, >30 mg/mmol)
- Available eGFR values (both before and after the value that requires imputation) of creatinine (hence eGFR) will be used as time-varying covariates (as exact values [to 1 decimal place]). Values before the maintenance randomisation will not be considered, nor any values on or after the date of failure of the transplant.
- Any characteristics associated with missingness

The imputation model will be stratified by the induction and maintenance therapy randomized allocations.

20 imputed datasets will be generated and then analysed using methods described in section 3.1.⁶ These 20 results will then be combined in order to produce an overall result using standard procedures.⁷ A complete case analysis will be conducted for comparison, but the primary emphasis will be placed on results after multiple imputation.

Any participant whose transplant has failed will be given an eGFR of 0 mL/min/1.73m² for all analyses after the date of failure. Sensitivity analyses will be conducted to vary this value of eGFR for failed transplants (range 0-10 mL/min/1.73m²). Participants who have died will have eGFR values imputed as for other missing values (and a sensitivity analysis conducted with 0 imputed for any such participants and if such participants are excluded from the analysis).

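### The primary ANCOVA leaves out proteinuria and blood pressure, two factors used to minimise the second randomisation, so its standard error may be slightly too large

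*SAP*

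**What the plan says.** Protocol 3.5 describes the allocation: "The second randomisation will be stratified by induction therapy allocation and minimized by prognostically-relevant criteria including graft function, proteinuria and blood pressure". The list is open-ended, so other factors may have been used.

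SAP 3.1 says the primary comparison of mean eGFR at 2 years "will use analysis of covariance (ANCOVA), adjusted for the baseline value". SAP section 2 adds: "All analyses will be stratified by induction therapy arm". The analysis therefore accounts for induction arm and graft function, but not for proteinuria or blood pressure.

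Proteinuria appears elsewhere in the SAP as a two-level covariate in the eGFR imputation model (3.2), as a subgroup factor (2.3) and as a secondary outcome (2.2). The SAP's analysis methods do not name blood pressure. Neither document explains the omission or plans a randomisation-based test.

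The imputation model does not make up for it. SAP 3.2 says "20 imputed datasets will be generated and then analysed using methods described in section 3.1", so the same two covariates are absent from every ANCOVA that is pooled.

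**The concern.** Minimising on a prognostic factor makes the arms more alike on that factor than simple randomisation would, so the treatment estimate varies less from trial to trial. A model without the factor leaves its variation in the residual and reports a standard error as if that balance had been left to chance. The reported standard error then exceeds the true one.

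This happens only if proteinuria and blood pressure add to the prediction of 2-year eGFR once baseline eGFR and induction arm are known. The protocol calls the minimisation criteria prognostically relevant as a group. It does not say that these two add anything to graft function, so the effect may be zero.

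What is at stake is the width of the interval and the size of the test in the single primary comparison. The estimate is not biased, and the error is in the conservative direction.

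**Working it through.** **The plan's own power figure.** Protocol 2.5 claims power above 90% at alpha 0.05 and above 80% at 0.01 with 800 patients, for a 10 mL/min difference and about 75% adherence. This cannot be reproduced, because neither the SD nor the share entering the second randomisation is given. Assuming a diluted difference of 10 × 0.75 = 7.5 mL/min and 60% of 800 randomised (240 per arm), power at 0.05 is 98%, 91% and 78% for an SD of 20, 25 and 30. The concern does not depend on this figure.

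**Closed form, perfect balance.** Let R² be the share of residual variance (given baseline eGFR and induction arm) that proteinuria and blood pressure explain. The documents give no value, so 0 to 10% is assumed. The low end is likelier, because Protocol 3.5 excludes patients with a protein:creatinine ratio above 80 mg/mmol, which narrows the range of proteinuria.

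- Reported SE / true SD = 1/√(1 − R²)
- True two-sided alpha = 2[1 − Φ(1.96/√(1 − R²))]; coverage = 1 − alpha

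| R² | SE / SD | True alpha | Coverage of 95% interval |
|---|---|---|---|
| 0 | 1.000 | 0.0500 | 95.0% |
| 1% | 1.005 | 0.0489 | 95.1% |
| 2% | 1.010 | 0.0477 | 95.2% |
| 5% | 1.026 | 0.0443 | 95.6% |
| 10% | 1.054 | 0.0388 | 96.1% |

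**Simulation, imperfect balance.** Assumptions: 400 patients, three continuous factors cut at tertiles for the minimisation, an 80% biased coin within induction arm, complete data, 40,000 replicates. Monte Carlo error is 0.0011 on alpha and about 0.35% on an SD (1/√80,000).

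| R² | True SD, omitted | Mean reported SE, omitted | True SD, adjusted | Mean reported SE, adjusted | Alpha, omitted | Alpha, adjusted |
|---|---|---|---|---|---|---|
| 0 | 0.1001 | 0.0999 | 0.1001 | 0.1000 | 0.0497 | 0.0497 |
| 1% | 0.0997 | 0.0999 | 0.0996 | 0.0995 | 0.0490 | 0.0497 |
| 2% | 0.0994 | 0.0999 | 0.0991 | 0.0990 | 0.0484 | 0.0497 |
| 5% | 0.0982 | 0.0999 | 0.0976 | 0.0975 | 0.0457 | 0.0497 |
| 10% | 0.0963 | 0.0999 | 0.0950 | 0.0949 | 0.0418 | 0.0497 |

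At R² of 1, 2, 5 and 10%, omitting the factors makes the reported SE too large by 0.2, 0.6, 1.8 and 3.8%. Adjusting cuts the true SD by only 0.1, 0.2, 0.6 and 1.3%. (The rounded table entries reproduce these percentages to within about 0.1 point.) Most of the real precision is already secured by the minimisation; adjustment mainly makes the reported SE the right size. Bias was about 0.0005 SD with or without adjustment, within Monte Carlo error.

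**Sensitivity to how the factors act.** A second simulation used three-level factors (400 patients, the same 80% coin, 12,000 replicates). At R² of 2, 5 and 10% the SE was too large by 1.0, 2.5 and 5.1%, with alpha 0.046, 0.043 and 0.038. These sit close to the closed form. The smaller figures in the table above are what one would expect when prognosis follows the exact value and only the category is balanced.

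**Multiple imputation.** The first simulation was repeated with an assumed 15% of outcomes missing completely at random, 20 imputations stratified by both allocations, all three factors in the imputation model, Rubin's rules and 8,000 replicates (Monte Carlo error 0.0024). At R² of 2, 5 and 10%, alpha was 0.047, 0.045 and 0.042 with the factors omitted from the ANCOVA, and 0.048, 0.051 and 0.052 with them included. The pattern carries over. Deaths, and failed grafts scored as 0, were not modelled.

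**Power.** 80% power at alpha 0.01 corresponds to an effect of 2.576 + 0.842 ≈ 3.417 reported SEs, hence Φ(3.417 − 1.960) = 92.8% at 0.05. With the factors omitted under perfect balance, power is Φ(1.457/√(1 − R²)) = 92.9, 93.0, 93.3 and 93.8% at R² of 1, 2, 5 and 10%. A test that includes the factors, held to the same true alpha, has the same power. No planned power figure is threatened, and no sample-size gain is claimed.

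**The case against.** The strongest reply is that nothing material follows. The estimate is unbiased, the test errs on the safe side, power does not fall below plan, and the effect may be zero. At R² of 1 to 2%, the likelier end, the SE is too large by 0.2 to 0.6%. The first figure is inside Monte Carlo error and the second is under two Monte Carlo errors. The minimisation factor closest to the outcome, baseline eGFR, is already in the model, as is the stratification factor. The size rests wholly on assumed inputs: R², the coin probability, the factor categories, the number randomised and the amount of missing data.

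All of this stands as an argument about size, and it is why the point is minor. It does not remove the omission or change its direction. The two simulations differ by a factor of less than two, and both show the SE too large and alpha restored by adjustment.

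A narrower objection concerns the imputation model. SAP 3.2 says of eGFR: "Values before the maintenance randomisation will not be considered". SAP 3.1 allows a baseline sample from the day of randomisation, so same-day baselines are arguably admissible and only earlier ones are ruled out. That is fair. The wording still needs settling, but the case for changing the ANCOVA does not depend on it.

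**Conclusion.** The concern holds, as a minor point. Two named minimisation factors are absent from the primary ANCOVA and from each imputed-data analysis. If they predict 2-year eGFR beyond baseline eGFR and induction arm, the reported SE is too large: by 0.2 to 3.8% in the continuous-factor simulation for R² of 1 to 10%, and by up to 5.4% under perfect balance at R² of 10%. The corresponding true alpha is 0.049 to 0.042, or 0.039 at the perfect-balance extreme. If they add nothing, nothing changes.

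The size rests on the assumed R² range and on an assumed form of minimisation, since the protocol gives neither the categories nor the coin probability. The direction does not rest on these details.

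**What to change.** Before unblinded analysis, specify the primary ANCOVA in SAP 3.1 with maintenance allocation, induction arm, baseline eGFR, baseline proteinuria, baseline blood pressure and any other factor actually used in the second minimisation. Fix the form of each covariate in advance, which also closes off a later data-driven choice of adjustment.

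In SAP 3.2, name the same covariates in the eGFR imputation model. At present blood pressure could enter only if it proved to be associated with missingness. State explicitly that the baseline eGFR defined in 3.1 is admitted, whether taken before or on the day of the maintenance randomisation.

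Keep the ANCOVA adjusted for baseline eGFR only, stratified by induction arm, as a sensitivity analysis. If the factors are to stay out of the primary model, the least the SAP should do is give the reason.

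The cost is SAP wording. Protocol 3.4.2 says "Blood pressure will be recorded at all follow-up visits", and proteinuria is needed to check eligibility for the second randomisation under Protocol 3.5, so the values should already be available.

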3.2 Missing data

It is likely that values of creatinine will be missing at random (as they will be collected via the UK Transplant Registry and it is very unlikely that their randomized allocation would affect whether a hospital provides data to the registry). Baseline characteristics of those participants with available and those participants with missing data will be compared to identify any characteristics associated with missingness. The amount of missing data at various timepoints after transplantation will be displayed graphically.

Missing eGFR values will be imputed using a multiple imputation model, using baseline covariates of:

- Age (calendar year)
- Sex
- Type of transplant (living donor, donor after brain death and donor after cardiac death)
- Donor age (calendar age)
- Proteinuria at baseline (in categories: ≤ 30 mg/mmol, >30 mg/mmol)
- Available eGFR values (both before and after the value that requires imputation) of creatinine (hence eGFR) will be used as time-varying covariates (as exact values [to 1 decimal place]). Values before the maintenance randomisation will not be considered, nor any values on or after the date of failure of the transplant.
- Any characteristics associated with missingness

The imputation model will be stratified by the induction and maintenance therapy randomized allocations.

20 imputed datasets will be generated and then analysed using methods described in section 3.1.⁶ These 20 results will then be combined in order to produce an overall result using standard procedures.⁷ A complete case analysis will be conducted for comparison, but the primary emphasis will be placed on results after multiple imputation.

Any participant whose transplant has failed will be given an eGFR of 0 mL/min/1.73m² for all analyses after the date of failure. Sensitivity analyses will be conducted to vary this value of eGFR for failed transplants (range 0-10 mL/min/1.73m²). Participants who have died will have eGFR values imputed as for other missing values (and a sensitivity analysis conducted with 0 imputed for any such participants and if such participants are excluded from the analysis).

Missing values of tacrolimus or sirolimus will also be imputed for any timepoint for which a value is expected but missing. The baseline variables used to impute missing values will include age, sex, type of transplant, donor age and any available values (as exact values to 1 decimal place) that occur after the maintenance randomisation but before failure of the transplant.

Missing values of urine protein:creatinine ratio will be imputed using baseline age, sex, type of transplant, randomized treatment allocations, available PCR values, angiotensin converting enzyme inhibitor or angiotensin receptor blocker use at baseline, diabetes status and cause of kidney

disease. Missing values for lipid fractions will be imputed using baseline age, sex, randomized treatment allocations, PCR at baseline, diabetes status and statin use at baseline.

All multiple imputation analyses will be implemented using SAS procedure MI. The expectation-maximization algorithm (which assumes a multivariate normal distribution) will be used to impute values (as eGFR is a continuous variable with an approximately normal distribution).

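### The eGFR imputation model does not guarantee several of the SAP's own subgroup factors, so on imputed data true subgroup differences in the sirolimus effect are pulled towards zero

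*SAP*

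**What the plan says.** SAP section 2.3 lists the subgroups in which the primary outcome, eGFR, will be assessed at 2 years and again at a median of 5 years. They include four categories of HLA mismatch, "Sensitization status (high versus normal determined by calculated reaction frequency", "First and subsequent transplants", three categories of baseline eGFR, and "Categories of baseline proteinuria (urine protein:creatinine ratio <30, ≥30 <50, ≥50 mg/mmol".

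SAP section 3.2 sets out the imputation: "Missing eGFR values will be imputed using a multiple imputation model, using baseline covariates of" age, sex, type of transplant, donor age, "Proteinuria at baseline (in categories: ≤ 30 mg/mmol, >30 mg/mmol", and the available eGFR values. Values from before the maintenance randomisation are not to be used. A last item brings in "any characteristics associated with missingness", found as follows: "Baseline characteristics of those participants with available and those participants with missing data will be compared to identify any characteristics associated with missingness". Treatment is handled by stratification: "The imputation model will be stratified by the induction and maintenance therapy randomized allocations".

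Failed grafts are set to an eGFR of 0, and participants who have died are imputed like other missing values. A complete-case analysis is planned for comparison, with the emphasis on the imputed result. The SAP does not say outright that the subgroup analyses use the imputed data. It is the natural reading, because section 2.1 defines the primary outcome with missing values imputed.

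**The concern.** An imputation model should contain the terms that the later analysis tests. Imputing within allocation cells keeps a treatment-by-covariate difference only for covariates that are in the model. Induction allocation, sex and donor type are protected, and age largely so. For a factor that is absent, each imputed value is drawn around the average for its arm, and only other post-randomisation eGFR values carry any subgroup signal.

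The direction matters because SAP section 3.4 applies the overall effect to a subgroup unless that subgroup is clearly different. Attenuation favours this default. Deaths add to the imputed fraction, and more will have accrued by the 5-year repeat.

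Baseline eGFR is a related gap. It is a listed subgroup and the ANCOVA covariate in SAP section 3.1, yet section 3.2 keeps values from before the maintenance randomisation out of the imputation.

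**Working it through.** The plan states no figure on this point, so there is none to reproduce. The check is of the mechanism and its size.

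**Factors side by side**

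| SAP 2.3 subgroup | In the SAP 3.2 model? |
|---|---|
| Induction, sex, donor type | Yes |
| Age (<60, ≥60) | Yes, not cut at 60 |
| HLA mismatch, sensitisation, first/subsequent transplant | Only if associated with missingness |
| Proteinuria <30, ≥30 <50, ≥50 mg/mmol | Only the split at 30 |
| Baseline eGFR | Values before maintenance randomisation barred |

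**Inputs.** All are assumptions, because the documents give none of them: true interaction δ = 10 mL/min, subgroup prevalence 20%, SD 15, missing fraction m = 5% to 30% completely at random, and correlation of an interim eGFR with the 2-year value 0.70 or 0.85. The interim value carries a share f = 0, 0.5 or 1 of the interaction. Imputation is by regression within maintenance arm on the interim value, followed by ANCOVA with a treatment-by-subgroup term.

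**Rule.** With b the imputation slope (about the correlation, since both values have the same SD):

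estimate ≈ δ × [1 − m × (1 − f × b)]

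- m = 0.30, f = 0: 10 × (1 − 0.30) = 7.0. Simulated: 7.02 and 6.92.
- m = 0.20, f = 0.5, b = 0.85: 10 × (1 − 0.20 × 0.575) = 8.85. Simulated: 8.70.
- m = 0.30, f = 1, b = 0.70: 10 × (1 − 0.30 × 0.30) = 9.1. Simulated: 9.28.

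**Estimated interaction with the factor omitted** (true value 10; correlation 0.70 / 0.85; simulation error about 0.1 to 0.2)

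| Missing | Interim carries none | Half | All |
|---|---|---|---|
| 5% | 9.52 / 9.36 | 9.64 / 9.80 | 9.96 / 9.88 |
| 10% | 9.10 / 9.07 | 9.43 / 9.61 | 9.70 / 9.84 |
| 20% | 7.87 / 8.01 | 8.72 / 8.70 | 9.34 / 9.76 |
| 30% | 7.02 / 6.92 | 8.05 / 8.40 | 9.28 / 9.53 |

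With the factor in the model the estimates were 9.86 to 10.15. Complete-case estimates were 9.80 to 10.19.

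**Trial-sized runs.** With 400 participants and a true interaction of 6 mL/min, half of it visible at month 12, 20% in the subgroup and correlation 0.8, the loss at 10%, 20% and 30% missing was about 5%, 13% and 18% when month-12 eGFR was always available. It was about 10%, 21% and 29% when month-12 eGFR was not available. A separate run with imputation in all four allocation cells and month-12 eGFR available gave roughly 5% to 17%. Adding the factor recovered the interaction within simulation error, at no cost to the main treatment effect even at 5% prevalence.

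**Proteinuria.** Assumed treatment effects of +4, 0 and −6 mL/min in the three categories, correlation 0.85. With only the split at 30, the <30 effect stayed at 3.9 to 4.0. The true gap of 6.0 between the upper two categories became 5.40 to 5.93 at 10% missing, 4.92 to 5.68 at 20%, and 4.04 to 5.78 at 30%. With three levels in the model it was 5.89 to 6.07.

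**Against sampling error.** With 400 participants, 20% in the subgroup and equal arms, the four groups hold 160, 160, 40 and 40. The standard error of the interaction is SD × √(1/160 + 1/160 + 1/40 + 1/40) = 0.25 × SD, or 2.5 to 3.75 mL/min for an assumed residual SD of 10 to 15. A 13% loss of 6 is 0.78 mL/min, which is 0.21 to 0.31 of a standard error.

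Baseline eGFR was not simulated; the point there rests on the same mechanism.

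**The case against.** The best reply has four parts.

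**The factors are not shut out.** A reader might infer that HLA mismatch, sensitisation and transplant number are excluded. They are not: the clause on "any characteristics associated with missingness" can admit them. That stands as a limit on the claim, but not as a remedy. The clause is data-dependent and selects predictors of missingness, not effect modifiers. In the simulations values were missing completely at random, where the clause would admit a factor only by chance, and the attenuation was still present. The SAP itself ties missingness to whether hospitals supply the registry, so patient-level factors may well not qualify.

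**Proteinuria is in the model.** This stands. Only the contrast above 30 mg/mmol is diluted. Protocol section 3.5 excludes ratios above 80 mg/mmol from the second randomisation, so the contrast is 30 to <50 against about 50 to 80.

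**The plan limits the loss.** Creatinine is recorded at the 9- and 12-month visits, values on either side of the missing one are used, any value within 6 months of the anniversary counts, and failed grafts are set to 0 and so are known. This makes the figures without interim eGFR a pessimistic bound. However, the 12-month visit comes only about six months after conversion and may carry only part of a 2-year difference.

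**The tests carry little weight.** They are tertiary, read with allowance for multiplicity, and the bias is small beside sampling error. This limits the importance of the point. The planned complete-case analysis would not show the attenuation if values are missing completely at random, but it is secondary and not specified for subgroups.

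**Conclusion.** The point holds as a limited one. The imputation model does not guarantee three prespecified subgroup factors, coarsens a fourth and bars the pre-randomisation values of a fifth. On imputed data a true treatment-by-subgroup difference in these factors is therefore pulled towards zero.

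The loss is at most about the fraction imputed. At an assumed 10% to 30% missing it is roughly 5% to 30% when interim eGFR carries none to half of the difference, and about 2% to 7% when it carries all of it. The missing fraction, interaction size, prevalence and correlations are all assumptions, and the subgroup analyses are taken to use the imputed data.

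Two stronger readings are not supported. A reader might infer that the primary comparison is biased; nothing here shows that, because imputation is stratified by maintenance allocation and the overall effect was not at fault in the check. A reader might also infer that these immunological factors are where conversion matters most. The documents do not say so: Protocol section 3.5 singles out eGFR below 40 for close monitoring and uses proteinuria and recent rejection as exclusions.

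**What to change.** In SAP section 3.2:

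- Make the section 2.3 subgroup factors fixed imputation covariates: HLA mismatch category, sensitisation, first or subsequent transplant, proteinuria as <30, ≥30 <50 and ≥50 mg/mmol, and baseline eGFR. Keep the missingness clause for anything further.
- Keep imputation stratified by both allocations, and prespecify a rule for sparse cells, for example collapsing over induction arm while keeping the maintenance arms separate.
- State that the subgroup analyses use the imputed data, and show complete-case subgroup results alongside.

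The cost is about seven extra parameters per cell: three for HLA mismatch and one each for sensitisation, transplant number, the extra proteinuria level and baseline eGFR. If 400 participants entered the second randomisation (an assumption), a cell would hold about 400 / 4 = 100. A factor with 5% prevalence would then have about 5 participants per cell, which is why the sparse-cell rule is needed. Interaction intervals will be somewhat wider.
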